## I. BACKGROUND & SIGNIFICANCE

### A. Historical Background

The scope of the problem: Heart failure (HF) is a common and progressively debilitating illness that affects nearly 6 million Americans. It has been associated with increased medical morbidity, including repeated hospitalizations, poor functioning, and reduced quality of life (QoL). Furthermore, it is costly; in 2010, it led to approximately \$39 billion in direct and indirect costs in the United States. Finally, HF is lethal, with studies estimating that 50% of HF patients die within 5 years of diagnosis.

The role of health behaviors in HF outcomes: Health behaviors significantly impact prognosis for patients with HF. Maintenance of a low sodium diet, adherence to medications, and increased physical activity have been associated with improved health, reduced hospital readmissions, and lower rates of mortality in HF patients. Exercise is particularly important, as exercise training programs have been associated with improved exercise capacity, QoL, and survival in randomized, controlled trials. As a result, the American Heart Association (AHA) recommends exercise training for all patients with chronic, stable HF.

However, many HF patients struggle with adherence to health behavior recommendations. Fifteen to 33% of patients with HF consume more sodium than is typically recommended. Up to 54% of HF patients have suboptimal adherence to their cardiac medications, and one-third to one-half of HF patients engage in physical exercise less than once a week. In sum, despite clear evidence that adherence may help to improve outcomes, patients with HF still struggle to complete health behaviors.

Interventions to improve health behaviors in HF: Interventions designed to increase adherence to health behaviors in HF have had mixed success, with systematic reviews suggesting that only half of interventions lead to improvements in QoL or hospitalizations. Less complex interventions in particular often have failed to impact readmissions or number of days in the hospital. Unfortunately, the intensity of more complex interventions (that require significant provider time) may make them cost-prohibitive.

Impact of psychological states on cardiac outcomes and health behaviors: Positive psychological states such as positive affect or optimism have been linked to improved long-term health outcomes, including reduced mortality, in healthy individuals and in those with cardiovascular disease. Numerous studies have confirmed the prospective association between positive states and mortality, oftentimes independent of negative emotional states and relevant medical factors. In one study of over 6,000 patients, greater positive affect was linked to a reduced risk of heart disease, even after controlling for health behaviors and depression. Similarly, in a study of over 97,000 women, baseline optimism was prospectively and independently associated with lower rates of incident coronary heart disease and mortality.

The impact of positive states on cardiac outcomes may be mediated in part by health behaviors. In a study of 773 elderly men, dispositional optimism was prospectively linked to more physical activity and higher intake of fruits and vegetables. Other studies confirm the relationship between positive states and diet, physical activity, and medication adherence. Given these links, an intervention to boost positive emotional states has the potential to improve health behaviors and medical outcomes in the HF population.

Positive psychology (PP): PP is an area of study that aims to boost positive psychological states (e.g., optimism, gratitude, positive affect) through systematic exercises, such as

performing kind acts, writing a letter of gratitude, or using a strength in a new way. These exercises are easily delivered and completed, require minimal provider training, and can be delivered easily via telephone. In non-cardiac patients, these interventions increase well-being and reduce depression consistently and substantially.

Research suggests that PP interventions may be effective in cardiac populations. Positive affect induction, though not a formal PP exercise, has been associated with increased medication adherence and greater physical activity in hypertensive patients and in post-percutaneous coronary intervention patients, respectively. Furthermore, in a pilot trial by our group, a formal, 4-week PP intervention for cardiac inpatients was feasible, acceptable, and associated with greater numerical improvements in psychological outcomes compared to relaxation response and attentional control groups. In a second preliminary study in patients who had suffered an acute coronary syndrome (ACS), a PP intervention led to improvements in depression, anxiety, and positive affect compared to treatment as usual.

However, aside from our research group's work, no studies have evaluated formal PP interventions to promote health behaviors in cardiac patients in general or HF patients in particular. Such interventions have the potential to leverage positive psychological states to improve health behaviors in this high-risk group of patients. Further study of these interventions is critical to determine how they can be applied to HF patients.

To address this question, we recently completed qualitative interviews with 32 HF patients (IRB # 2015P000069) to better understand their HF symptoms, examine the relationships between positive psychological constructs and health behaviors, and identify barriers and facilitators to completing health behaviors. The information gained from these interviews allowed for the creation of an intervention that was adapted to this specific population. Next, we performed a single-arm, proof-of-concept trial (N=11, IRB#2016P001443) to examine the feasibility of the intervention and our outcome measures, as well as to gain preliminary feedback from participants. Based on this information, we have created an optimized, 12-week, telephone-delivered, PP-based health behavior intervention and aim to examine its feasibility, acceptability, and preliminary impact in a group of patients with mild to moderate HF in a randomized, controlled pilot trial.

## **B. Preliminary Studies**

[name] is ideally suited to complete the proposed study given his prior research experience. He has been co-investigator for both observational and intervention studies focusing on positive psychological states in cardiac patients, and he was the principal investigator (PI) of a PP intervention trial in psychiatric inpatients with bipolar depression. The studies below demonstrate his ability to perform the proposed trial.

**Preliminary Studies #1: Observational and Intervention Studies in Cardiovascular Disease.** As part of the Cardiac Psychiatry Research Program (CPRP) team, [name] has served as a co-investigator for a number of intervention studies to investigate the use of psychological interventions in hospitalized patients with cardiac disease. This includes a large (N=175) collaborative care depression management trial and a recently completed collaborative care study (N=183) for depression or anxiety disorders in patients with HF and other cardiac diseases. These two studies have provided experience with the recruitment, enrollment, and retention of participants with heart disease and with many of the outcome measures that will be used in the proposed study.

**Preliminary Studies #2: Positive Psychology Interventions.** [name] also has experience with PP interventions in non-cardiac populations. He served as a co-investigator for a study involving the systematic administration of PP exercises to psychiatric inpatients (N=61) with suicidal ideation. In this study, 189/213 (88.7%) assigned exercises were completed, suggesting that the intervention was feasible and acceptable. More recently, [name] was the Principal Investigator of a study to develop a telephone-based PP intervention for psychiatric inpatients with bipolar depression, and he successfully recruited 45 participants over the first two phases of the study. He also has served as the Project Director for two PP intervention trials—one in depression, the other in diabetes. These studies introduced [name] to the measurement of positive psychological states using the same tools as those for the proposed study (e.g., LOT-R, PANAS), gave him experience with delivering PP interventions via telephone, and demonstrated our team's ability to retain a high percentage of patients despite their level of risk and psychiatric illness.

**Preliminary Studies #3: Positive Psychological States in Cardiovascular Disease.**

Finally, [name] work as a co-investigator in the CPRP has exposed him to the study of positive psychological states in patients with cardiovascular disease. In a pilot study, our team developed and tested an 8-week PP intervention to cultivate gratitude, optimism, and kindness in 30 cardiac inpatients (N=9 in the PP group) and found the PP intervention to be feasible and well-accepted. Furthermore, [name] played an active role in a prospective, observational study (N=212) to examine the associations between positive psychological states and health behaviors in post-ACS patients. Results from this study suggest that higher levels of optimism are prospectively associated with greater physical activity and reduced cardiac readmissions 6 months later. [name] also serves as the Project Director of a study to examine the use of PP interventions in post-ACS patients. Results from the first stage of this study suggest that in the post-ACS period, patients view positive emotions as promoters of health behaviors. In the second phase of this study, an 8-week, telephone-based PP intervention led to greater improvements in depression, anxiety, and positive affect, compared to treatment as usual.

Finally, [name] is the PI of an ongoing study to examine the feasibility and potential utility of a PP- based intervention to improve health behavior adherence in patients with New York Heart Association (NYHA) class I, II, or III HF (IRB# 2016P001443). After successfully completing qualitative interviews in 32 HF patients, [name] developed a 10-week PP-based health behavior intervention for this population, and tested it in a proof-of-concept trial. Though follow up for this trial is still ongoing, preliminary analyses involving the first five participants revealed that the intervention was feasible (with 100% of exercises completed), easy to complete, and subjectively helpful. Furthermore, the intervention led to numerical improvements in both positive affect and daily moderate to vigorous physical activity. Now, [name] is using the information from the first two phases of this trial to inform his proposed randomized-controlled trial of this PP-based health behavior intervention for HF patients. [name] involvement in these studies has provided him with information about the links between positive states and outcomes in cardiac patients, experience with developing and delivering a PP-based health behavior intervention, and experience with the outcome measures and accelerometers to be used in the proposed study.

**Relevance of Preliminary Work to the Proposed Project:** [name] now has experience recruiting and retaining patients at Massachusetts General Hospital (MGH) who have HF and other cardiac illnesses, measuring psychological and medical variables effectively, and

developing interventions to increase positive psychological states. These experiences make him well-positioned to successfully and efficiently complete the proposed project.

### **C. Rationale/Potential Benefits/Overview of Proposed Research**

**Intervention to increase positive emotions and promote health behaviors in cardiac patients.** There is clear evidence linking positive emotions with superior cardiac outcomes. Despite this, there has been minimal study of interventions in cardiac patients that specifically focus on the cultivation of positive emotional states. Though some programs have utilized relaxation or mindfulness, PP interventions had never been used in patients with HF until our pre-pilot study, despite their well-documented overall efficacy. Indeed, aside from our team's work to develop a PP-based intervention for post-ACS patients, we are aware of only one other trial that used PP in any cardiac population (outpatients with hypertension or undergoing angioplasty).

To address this gap in knowledge, we have created and optimized a novel PP-based health behavior intervention for patients with HF. A treatment cultivating positive emotions in this vulnerable population could provide broad and significant health benefits, and may have distinct—and more powerful—effects than simply attempting to dampen negative emotions. In the first phase of treatment development (IRB # 2015P000069), we performed qualitative research (N=32) to: (a) assess barriers to health behavior completion, (b) identify the causes and extent of positive emotional deficits, (c) examine potential links between positive emotional deficits and impaired health behaviors, and (d) inquire about the utility of potential PP and goal-setting exercises in participants with NYHA class II or III HF. Using this information we developed a customized, PP-based health behavior intervention based on these results and the existing literature, which we tested during phase two of this project (IRB # 2016P001443). Though follow-up is ongoing, preliminary analyses after 5 participants revealed that the intervention was feasible, subjectively helpful, and associated with significant immediate improvements in happiness and numerical improvements in positive affect and moderate to vigorous physical activity. Using feedback from participants and the data from this proof-of-concept trial, we have created an optimized version of the intervention. We now wish to test the feasibility and efficacy of the optimized intervention in a three-arm, randomized pilot trial.

#### **In this project, we hope to do the following:**

1. Test a 12-week, telephone-delivered health behavior intervention utilizing PP exercises and systematic goal-setting in a three-arm, randomized, controlled pilot trial in patients with mild to moderate HF (N=75).
2. Determine whether this optimized intervention is feasible in a small cohort of HF patients.
3. Explore potential benefits of the intervention on outcomes of interest (e.g., psychological health, functioning, and health behavior adherence) compared to a motivational interviewing- (MI) based education condition and treatment as usual (TAU).

## **II. SPECIFIC AIMS**

**Specific Aim #1 (Feasibility [primary outcome], acceptability, immediate impact):** To assess the feasibility, acceptability, and immediate impact of the PP-based health behavior intervention

on optimism and happiness in a three-arm (N=75), randomized, controlled pilot trial.

*Hypothesis: The PP intervention will be feasible (the majority of participants will complete at least 7 of 12 sessions/exercises) and acceptable (mean score of at least 6 out of 10 on ratings of ease of completion and subjective helpfulness of the exercises) and will have adequate immediate impact on positive affect and optimism (post-exercise ratings of positive affect and optimism will be higher than pre-exercise ratings (measured by pre- and post- measurements on a Likert scale).*

**Specific Aim #2 (overall impact on psychological health):** to examine the intervention's overall impact on both positive (positive affect, optimism) and negative (depression, anxiety) psychological health, compared to TAU and an MI-based educational control condition.

*Hypothesis: The intervention will lead to significant pre-post increases in positive affect and optimism and significant reductions in depression and anxiety. Compared to the control conditions, the PP-based intervention will lead to greater numerical improvements in all psychological outcomes.*

**Specific Aim #3 (adherence and functional outcomes):** To examine the impact of the intervention on physical activity (steps, as measured by accelerometer; primary health behavior outcome), medication adherence, sodium intake, HF-related QoL, and generic HRQoL, compared to TAU and an MI-based educational control condition.

*Hypothesis: The intervention will lead to significant pre-post improvements in adherence and functional outcomes at follow-up and will lead to greater numerical improvements in these outcomes compared to the treatment as usual and the MI-based control condition.*

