### III. PARTICIPANT SELECTION

#### A. Inclusion/Exclusion Criteria

##### **Inclusion criteria:**

- Adult patients with NYHA class I, II, or III HF admitted to an MGH inpatient unit or outpatients at the MGH Heart Center or MGH-affiliated primary care clinic. Patients with NYHA class IV HF have ongoing HF symptoms at rest, making it difficult for them to increase physical activity and other health behaviors; therefore, they will not be included. HF diagnosis will be confirmed via chart review and with the patient's treatment team as needed. NYHA class will be confirmed with the patient and adjudicated by [name] or the patient's treatment team when necessary.
- Suboptimal adherence to health behaviors. This will be defined as a total score of  $\leq 15$  on three Medical Outcomes Study Specific Adherence Scale (MOS) items regarding diet/exercise/medications. The MOS has been used in multiple prior studies assessing adherence in cardiac patients, including our own studies in this population. This threshold score on the MOS will ensure that all participants will have the potential to improve their health behaviors.

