**Exclusion criteria:**

- Cognitive deficits impeding a participant's ability to provide informed consent or participate, assessed via a 6-item cognitive test that is sensitive and specific for screening for cognitive impairment in research participants.
- Medical conditions precluding interviews or likely to lead to death within 6 months.
- Inability to speak English, inability to read or write, inability to walk, or lack of a telephone.

**Justification for inclusion and exclusion criteria:** We will recruit individuals over age 18 that have NYHA class I, II, or III HF and endorse suboptimal adherence to physical activity, diet, and/or medication use. We will study HF because it is extremely common and has been associated with poor functioning and high rates of mortality (50% of individuals with HF die within 5 years of diagnosis). We chose NYHA class I, II, and III HF patients because class II and III patients comprise the majority of participants in studies that identify links between physical activity and improved exercise capacity, QoL, and survival and because class I patients also likely would benefit from increases in physical activity and health behaviors. We did not include NYHA class IV patients because they may be too physically impaired to perform some of the PP and health behavior exercises included in the intervention.

We will focus on adherence to health behaviors in HF for several reasons. First, adherence to health behaviors is associated with better HF outcomes, including lower rates of mortality, but patients with HF often struggle to adhere to these behaviors. Second, existing interventions to improve health behaviors are costly and have had limited impact on medical outcomes and QoL. Finally, positive psychological states have been associated with improved adherence to health behaviors in healthy and other medically ill populations, suggesting that an intervention to boost these states in HF patients may be an effective way to improve these behaviors and medical outcomes in general. We will enroll only those patients who have at least mild deficiencies in health behaviors.

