**Table 1. Schedule of study events.**

	Pre-enrollment	Initial Visit	Second in Person Visit	Phone Sessions (12 weeks)	Follow-up Phone Call (Week 12)	Follow-up Phone Call (Week 24)
Cognitive screen	X					

Chart review to confirm eligibility	X					
Assessment of inclusion criteria (MOS, NYHA class)	X					
Chart review for baseline characteristics		X				
Randomization to PP or Control Condition			X			
Weekly intervention exercises*			X	X		
Exercise ratings			X	X		
Self-report measures (SSQ, SRMA, MOS, LOT-R, PANAS, HADS, KCCQ, SF-12, SOM)		X			X	X
Objective adherence data (ActiGraph step counter)		X			X	X
Satisfaction with Care					X	X
Hospital Readmissions					X	X

\*Type of exercise assigned will depend on whether participant is in PP-MI or control condition

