**Measures:**

- HF-related QoL: KCCQ
- HF symptoms: KCCQ subscale
- Health related quality of life: SF-12
- Self-reported adherence: MOS
- Physical activity: ActiGraph accelerometer
- Medication adherence: SRMA
- Sodium intake: SSQ

We will examine between-group differences (PP-based condition vs. MI-informed educational control and PP-based condition vs. TAU) on changes in functional outcomes and health behaviors to assess the impact of the intervention compared to both an active control and TAU.

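### The Aim 3 hypothesis credits a significant pre-post rise in adherence to the intervention, although patients are admitted for a low score on the MOS items that are also an Aim 3 outcome; regression to the mean can inflate that limb

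*Combined protocol and SAP*

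**What the plan says.** **Hypothesis.** In section II the Aim 3 hypothesis has two limbs in one sentence. The first is "The intervention will lead to significant pre-post improvements in adherence and functional outcomes at follow-up". The second is that the intervention "will lead to greater numerical improvements in these outcomes compared to the treatment as usual and the MI-based control condition". Only the first limb asks for significance; the second asks for a numerical lead.

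**Entry.** Section III.A requires a total of 15 or less on three MOS items covering diet, exercise and medication. The stated reason is "This threshold score on the MOS will ensure that all participants will have the potential to improve their health behaviors". The justification that follows the exclusion criteria adds "We will enroll only those patients who have at least mild deficiencies in health behaviors".

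**Outcomes.** The Aim 3 measures in section VI.A and B include "Self-reported adherence: MOS". Section V.E says these are the diet, exercise and medication items, with recall over the last month. The main health behavior measure is a different one: "physical activity (steps, as measured by accelerometer; primary health behavior outcome".

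**Timing.** Table 1 lists the MOS before enrollment, under "Assessment of inclusion criteria (MOS, NYHA class", and again at the initial visit and both follow-ups, under "Self-report measures (SSQ, SRMA, MOS, LOT-R, PANAS, HADS, KCCQ, SF-12, SOM". Section V.E places the initial-visit MOS among the baseline data.

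**Analysis.** For Aim 3, VI.A and B compare change in PP with change in MI and in TAU. VI.C uses a rank sum test between groups for steps and random-intercept models of between-group differences in change for the self-report scales, two-tailed at 0.05. Section VI specifies no within-arm test for Aim 3. VI.D assumes 20 participants per group and says the trial is not designed to detect between-group differences in health behavior outcomes.

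**The concern.** A group chosen because its measured score is low tends to score higher when measured again, even if nothing has changed. Here the scale that decides entry is also an outcome, and the first limb reads a significant rise in one arm as something the intervention brought about. The protocol presents the threshold as leaving room to improve; it does not mention that the threshold also creates an expected rise.

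The trial disclaims power for between-group health behavior effects, and the second limb needs no significance. The within-arm limb is therefore the part of the hypothesis most likely to be reported as significant. If it were used as written, an inert programme could be described as having improved self-reported adherence and be taken into a larger trial on that basis.

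**Working it through.** **The plan's own figures.** Section VI.D gives no power or error figure for Aim 3, so there is none to reproduce on this point. Its feasibility figure does reproduce: with 20 PP participants and 80% against 50%, the exact rule of at least 15 of 20 has two-sided alpha 0.041 and power 80.4%.

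**Inputs from the documents.** 20 per arm; two-sided 0.05, hence 2.5% in the direction of improvement; entry by truncation on the screening MOS; MOS repeated at the initial visit.

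**Assumptions, because the documents give no values.**
- Share of screened patients who qualify, q: 0.5 to 0.8.
- Correlation of screening with initial-visit MOS, r(SB): 0.9. It is set high because the one-month recall windows overlap when the two are close together.
- Correlation of follow-up MOS with the screening score, r(SF), and with the initial-visit score, r(BF): 0.65 to 0.70 for both.
- Scores jointly normal, no treatment effect, paired t-test in the PP arm. The plan names no test for this limb.

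**Step 1: expected rise, in SDs of the unselected population.** With cut-point c = Φ⁻¹(q) and λ = φ(c)/q, shift = [r(SB) − r(SF)] × λ.
- q = 0.5: c = 0, λ = 0.798. Shift = 0.20 × 0.798 = 0.16, or 0.25 × 0.798 = 0.20.
- q = 0.8: c = 0.842, λ = 0.350. Shift = 0.20 × 0.350 = 0.07, or 0.25 × 0.350 = 0.09.

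**Step 2: chance of a significant rise.** The variance of the change among those admitted is 2 − 2r(BF) − [r(SB) − r(SF)]² × (1 − v), where v = 1 − cλ − λ² is the variance of the truncated screening score (0.363 at q = 0.5; 0.583 at q = 0.8). The t statistic has 19 degrees of freedom and noncentrality shift × √20 / SD.

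| q | r(SF) = r(BF) | Shift | SD of change | Noncentrality | Chance of significant PP rise |
|---|---|---|---|---|---|
| 0.5 | 0.65 | 0.20 | 0.813 | 1.10 | 18% |
| 0.5 | 0.70 | 0.16 | 0.758 | 0.94 | 14% |
| 0.8 | 0.65 | 0.09 | 0.821 | 0.48 | 7% |
| 0.8 | 0.70 | 0.07 | 0.764 | 0.41 | 6% |

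Simulation of 20,000 null trials per row agrees to within half a percentage point.

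**Step 3: independent error at the repeat.** If r(SB) equals r(SF), for example both 0.7, the bracket in step 1 is zero. The shift is zero and the chance is about 2.5%.

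**Step 4: both limbs together.** In the same simulations PP has the largest mean change of the three arms in about 33% of null trials. A significant PP rise together with a PP lead occurs in about 5-14%.

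**Step 5: the planned contrast.** A two-sample t-test of change, PP against TAU, used as a simple stand-in for the random-intercept model, rejects in about 5% of null trials in every scenario. All three arms pass the same entry threshold, so the expected rise cancels.

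**Step 6: scales not used for selection.** For another outcome correlated r with the screening MOS and ρ with itself over time, shift = r(1 − ρ)λ. With r of 0.3-0.5, ρ of 0.5-0.7 and 50-85% qualifying, the within-arm chance is about 4-14%. These correlations are also assumed.

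**The case against.** The strongest reply is that the plan already protects its inferences. The hypothesis does not stop at the pre-post limb, every Aim 3 analysis in section VI is between randomised groups, the main health behavior outcome is accelerometer steps rather than the MOS, and the MOS is measured afresh at the initial visit. The entry threshold is described as at least mild deficiency, so truncation may be light. The trial is a pilot, and no rule ties progression to a within-arm MOS change. All of this is correct, and it narrows the point considerably.

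It does not remove the point. The first limb still sets a significance criterion that section VI neither specifies nor guards. The second limb is weak protection, since chance alone gives PP the lead in about one null trial in three. The repeat MOS removes the drift fully only if its error is independent of the screening score. With one-month recall and, for inpatients, possibly little time between the two, that cannot be taken for granted.

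A reader might go further and infer three things that the documents do not support:
- *That regression to the mean alone can satisfy the Aim 3 hypothesis.* It acts equally on all three arms and gives PP no advantage in the second limb.
- *That the within-arm test is the only significance test for Aim 3.* VI.C plans between-group tests at 0.05.
- *That the screening score is the baseline.* That reading would give 9-37% with 50-80% qualifying and a follow-up correlation of 0.6-0.7, but section V.E and Table 1 place the baseline MOS at the initial visit.

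**Conclusion.** The concern holds for the first limb of the Aim 3 hypothesis, directly for the MOS and only through correlation for SRMA and SSQ. Selection on the MOS means that a significant within-arm rise is not good evidence of an intervention effect. With the documented initial-visit baseline, a false significant PP rise occurs in about 6-18% of null trials against a nominal 2.5%, given 50-80% qualifying, a screen-baseline correlation of 0.9 and follow-up correlations of 0.65-0.70. It stays near 2.5% if the repeat measurement has independent error. The mechanism is clear, but the documents give no MOS distribution, pass rate or retest correlation, so its size cannot be fixed from them.

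The between-group analyses are sound on this point. Aim 2 uses similar pre-post wording, but patients are not selected on its scales.

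**What to change.** In section II, remove the significant pre-post criterion from the Aim 3 hypothesis for self-reported adherence (MOS, SRMA, SSQ). State that any claim of an effect on adherence rests on the PP-minus-TAU and PP-minus-MI differences in change already planned in section VI, each with a 95% confidence interval. Add to VI.C that the PP pre-post change will be reported descriptively, beside the TAU and MI changes.

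This needs no new data, visits or patients. The cost is that a within-arm claim of significance is given up, and with about 20 per arm the between-group intervals will be wide. That width is consistent with the plan's own statement that it is not designed to detect these differences.
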